3.2 Secondary Objectives

Secondary efficacy objective: the study will examine the effects of ezogabine on clinical and behavioral measure of anhedonia, depressive symptoms, and suicide ideation in an exploratory manner. In addition, general functioning will be measured with the WHO Disability Assessment Schedule 2.0 (WHODAS 2.0; World Health Organization [WHO], 2012). Please, refer to sections 9 “Study procedures and guidelines” for more details.

Secondary safety objective: to examine the safety and tolerability of ezogabine in patients with depressive disorder.

4 STUDY DESIGN

4.1 Study Overview

This is a multi-center, phase IIa, parallel arm, double-blind, randomized, placebo-controlled, clinical trial. Forty-eight treatment-seeking patients with a primary diagnosis of depressive disorder according to Diagnostic and Statistical Manual of Mental Disorders-Fifth Edition (DSM-5; MDD, persistent depressive disorder, other specified depressive disorder), clinically significant anhedonia (defined SHAPS \geq 20) and at least moderate current illness severity (measured as Clinical Global Impression–Severity [CGI-S] Scale \geq 4) will be enrolled. Each subject will be randomly assigned to one of the treatment arms (ezogabine, placebo) in a 1:1 fashion under double-blind conditions; randomization will be under the direction of the coordinating center and stratified by center. Screening data will be reviewed by the site PI to determine subject eligibility. Subjects who meet all inclusion criteria and none of the exclusion criteria will be entered into the study. Study participants will undergo assessments at baseline then following study drug/placebo weekly for five weeks (titration period and primary outcome visit) and then after three weeks (taper period and exit visit). During the taper period participants will undergo weekly phone calls from a member of the study team to assess compliance and side effects. Please, refer to **Table 2** “Schedule of Assessments, Outcome Measures, Labs, and Procedures.”

Following screening and randomization, study participants undergo a 5-week medication titration schedule according to the FDA package insert. For more information about randomization, treatment and taper schedules please refer to section 8 “Study Treatments”.

The following treatment regimens will be used:

- Ezogabine group: ezogabine at 900 mg daily
- Placebo group: inactive compound daily.

Total duration of subject participation will be up to 14 weeks. Total duration of the study is expected to be 24 months.

5 CRITERIA FOR EVALUATION

5.1 Primary Efficacy Endpoint

Our primary efficacy endpoint is change in activation within the bilateral VS from baseline (Study Visit 0) to week 5 (Study Visit 5) as measured by fMRI during the IFT. Patients with depression show abnormal responses to reward expectancy and reward responsiveness within the cortico-striatal reward circuit (VS/mPFC/Anterior cingulate cortex [ACC]) and data from our pilot study on ezogabine showed that following treatment with ezogabine, brain responses to reward expectancy and reward responsiveness were enhanced. The VS is considered to be the principal reward related region and therefore functions as the primary region of interest (ROI). The right and left VS regions will be combined (averaged) into a single bilateral ROI as there are no laterality hypotheses regarding effect of treatment on the VS.

5.2 Secondary Efficacy Endpoints

Similarly to the primary efficacy endpoint, change in activation within other regions of the reward cortico-striatal circuit (for example, mPFC and ACC) from baseline to week 5 will be measured by fMRI during the IFT.

Clinical outcome

Change in clinical symptoms of anhedonia (as measured by the SHAPS, Temporal Experience of Pleasure Scale [TEPS], Specific Loss of Interest and Pleasure Scale [SLIPS], Anticipatory and Consummatory Interpersonal Pleasure Scale [ACIPS] and on depressive symptoms assessed through clinical ratings scales (Montgomery-Asberg Depression Rating Scale [MADRS]). Global illness improvement and severity will be evaluated through changes in CGI-I and CGI-S scores. The level of disability and functioning will also be investigated via the World Health Organization Disability Assessment Schedule (WHODAS 2.0). For more details on the clinician and self-report measure that will be administered, please refer to section 9 “Study procedures and guidelines”, paragraph 9.1.6 “Other clinical procedures”.

Behavioral outcome

Change in behavioral symptoms of anhedonia will be captured through a computer-based task, the Probabilistic Reward Task (PRT). In this task, a signal detection theory approach is used, whereby subjects must discriminate between two ambiguous stimuli, displayed

rapidly on a computer screen, in order to receive a monetary reward. Unbeknownst to the subjects, correct identification of one stimulus is reinforced three times more frequently than the other stimulus. Under these experimental circumstances, healthy subjects reliably develop a response bias (that is, preference) for the stimulus that is reinforced more frequently, regardless of which stimulus was actually presented. Thus, reward responsiveness assessed in this task reflects the rapid shaping of future behavioral choices based on prior reinforcement experiences. Subjects with MDD and healthy subjects with elevated depressive symptoms fail to develop this biased response for the more frequently reinforced stimulus, and tend to respond similarly to both stimuli, reflecting decreased responsiveness to rewards. Moreover, response bias was found to predict current and future anhedonic symptoms in both nonclinical and clinical samples. For more details on PRT, please refer to section 9 “Study procedures and guidelines”, paragraph 9.1.6 “Other clinical procedures”.

5.3 Safety Evaluations

Safety will be monitored by the evaluation of potential adverse events, clinical laboratory test results, vital signs measurements, physical examination, ECG and ophthalmological findings. Our safety evaluations include frequency and severity of observed adverse events over the study treatment period. The frequency and severity of adverse events will be compared between the treatment conditions. For a complete discuss of risks associated with the study drug, please see section 2.1 “Risk/Benefit Assessment”. For a complete discussion of study procedures, please see section 9 “Study Procedures and Guidelines”. Below, we outline specific safety evaluations conducted as part of the study protocol.

Monitoring for Worsening Depression and Suicidal Ideations or Behaviors

Participants will meet with a study clinician weekly during the treatment period. The interval medical history will be obtained and adverse events, changes to concomitant medications and dosing compliance will be recorded. Suicidal ideation and behavior will be specifically assessed, including a review of the Columbia Suicide Severity Rating Scale (C-SSRS) and the overall severity of symptoms will be monitored by the clinical global impression scale (CGI-S). If, at any point during the clinical trial, a participant will be assessed with a suicidal ideation with any intent or plan, as measured by a C-SSRS score of greater than 3 during the past week and/or with a CGI-S score ≥ 6 (indicating extreme illness severity) or a CGI-I score ≥ 6 (indicating an extreme worseness of the symptoms), the site PI, or his designee, will conduct a safety review to determine the appropriate course of action including whether acute intervention is needed and whether it is in the best interests of the subject to continue in the study.

Safety review: The safety review will consist of a separate review of safety and well-being of the participant by the site PI or his designee. This review will be documented by a Safety Review Form (SRF) that will be filed in the subject binder and that will consist of a brief description of the case and of the event that triggered the review. Outcome of the review will be the decision whether to continue or discontinue the subject from the protocol (if

this is the case, appropriate clinical care will be provided). In the eventuality the event satisfies the definition of an adverse event (AE) or of a serious adverse event (SAE), it will be reported accordingly. For more detail about adverse event monitoring and reporting, please refer to section 11 “Adverse experience reporting and documentation”.

Ophthalmological exams

All the participants will also undergo a complete ophthalmological exam at screening and at study end by a study ophthalmologist, to include the following procedures: Visual acuity, Color plates, Amsler grid, Visual field test, Dilated fundus exam, Fundus photography, and Ocular coherence tomography (OCT) of the macula. Should patient exhibit any changes in fundus exam and/or OCT from screening, they will undergo a fluorescein angiogram and possibly electroretinogram depending on the discretion of the Ophthalmologist. After cessation of medication the regularity of baseline dilated eye exams will be determined by the presence or absence of retinal pathology at the discretion of the Ophthalmologist.

Additional Safety Monitoring

In addition to the procedures described above, the following procedures are performed as part of the study safety evaluations. Medical history, current and past physical and psychiatric history, venous blood sampling for clinical laboratory tests (comprehensive metabolic panel, CBC, TSH), vital signs, urine toxicology, pregnancy test (if applicable), and ECG will be performed by qualified staff. For more information refer to sections 2.1 “Risk/Benefit Assessment” and 9 “Study Procedures and Guidelines”.

Provision of study follow-up for treatment emergent adverse events at study exit: in case of any adverse event (including, but not limited to suicidal ideation or behavior) present at the study exit visit, subject will be referred to follow-up care until the event is resolved and/or a stable care plan is in place. The site PI will follow up with the subject until the abnormal parameter or symptom has resolved or stabilized.

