2.1 Risk / Benefit Assessment

The most common adverse effects of ezogabine are dizziness (23%), drowsiness (22%) and fatigue (15%). No contraindications to treatment were reported in the manufacturer’s label. Since QT prolongation has been observed, ECG will be monitored at screening and study exit. Skin discoloration around the lips or nail bed, either blue or gray, has been reported and is estimated to affect up to 10% of patients treated for more than two years. Below we summarize the risks of the study drug and strategies to mitigate risk. In addition, please see section 5.3 “Safety Evaluation” for additional description of study safety evaluations.

QT Prolongation:

QT prolongation has been observed in healthy subjects during a randomized, double-blind study where the maximum mean increase of QT interval of 7.7 msec was observed at 3 hours after 22 days of treatment with ezogabine 1,200 mg daily. No effects on heart rate, PR, or QRS intervals were noted. In our trial, the dosage of 1200 mg daily will not be reached and participants will be at the highest dose of 900 mg per day, respectively, for one week. Moreover, since patients who are prescribed ezogabine with medicines known to increase QT interval or who have known prolonged QT interval, congestive heart failure, ventricular hypertrophy, hypokalemia, or hypomagnesemia should be observed closely, to ensure participants’ safety we will exclude from the trial subjects with:

- unstable medical illness including ischemic heart disease or other cardiovascular disease;
- history of QT prolongation or congenital QT syndrome
- prolonged QT interval at screening (QTc > 480 msec)
- clinically significant abnormalities of laboratory tests and EKG

To reduce risks for participants in this trial, an EKG will be performed at the screening, at visit 4 (to monitor any QT effects that have emerged prior to escalating to the highest dose; see Section 10.3 “Double Blind Treatment Period” for additional details) and at study exit visits.

Skin Discoloration:

Skin discoloration around the lips or nail bed, either blue or gray, has been reported and is estimated to affect up to 10% of patients treated for more than two years. Given the limited exposure to the study drug in the current study, we anticipate the risk of skin discoloration to study participants will be very small.

Suicidality:

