Antiepileptic drugs (AEDs), including ezogabine, have been found to increase the risk of suicidal thoughts or behavior in pooled analyses. Pooled analyses of 199 placebo-controlled clinical trials (mono- and adjunctive-therapy) of 11 different AEDs showed that patients randomized to one of the AEDs had approximately twice the risk (adjusted relative risk 1.8, 95% confidence interval [CI]: 1.2, 2.7) of suicidal thinking or behavior compared to patients randomized to placebo. In these trials, which had a median treatment duration of 12 weeks, the estimated incidence of suicidal behavior or ideation among 27,863 AED-treated patients was 0.43% compared to 0.24% among 16,029 placebo-treated patients, representing an increase of approximately 1 case of suicidal thinking or behavior for every 530 patients treated. There were 4 suicides in drug-treated patients in the trials and none in placebo-treated patients, but the number is too small to allow any conclusion about drug effect on suicide. Suicide ideation and behavior will be monitored during the length of the study through clinical assessments at screening and exit visits, and weekly during the treatment period. The Columbia Suicide Severity Rating Scale (C-SSRS) will also be conducted at each study visit to monitor suicidal ideation and behavior. If, at any point during the clinical trial, a participant will be assessed with a suicidal ideation with any intent or plan, as measured by a C-SSRS score of greater than 3 during the past week and/or with a Global Clinical Impression – Severity Scale (GCI-S) score ≥ 6 (indicating extreme illness severity) or a Global Clinical Impression – Improvement Scale (CGI-I) score ≥ 6 (indicating an extreme worseness of the symptoms), a safety review will be performed by the site PI, or his designee, to determine the appropriate course of action including whether acute intervention is needed and whether it is in the best interests of the subject to continue in the study. For more information, refer to paragraphs 5.3 “Safety evaluations” and section 9 “Study Procedures and Guidelines”.

Other Adverse Effects:

Other side effects include urinary retention, neuropsychiatric symptoms (confusional state, psychotic symptoms, and hallucinations) and withdrawal seizures. To protect participants from these possible side effects the following actions will be completed:

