- urologic symptoms will be carefully monitored and a comprehensive evaluation of urologic symptoms prior to and during treatment with ezogabine will be completed;
- neuropsychiatric symptoms will be investigated at screening and ezogabine will be titrated on a 5-week period according to the FDA package insert in order to reduce the risk of psychosis and hallucinations; to monitor the impact of dizziness and somnolence, that usually occur during the titration phase, subjects will be evaluated on a weekly basis by a study physician;
- withdrawal symptoms will be prevented by a gradual withdrawal over a period of at least 3 weeks, unless safety concerns require abrupt withdrawal.

Retinal Changes:

The FDA had issued a black box warning regarding the potential for retinal abnormalities following treatment with ezogabine, with an unknown relationship to vision loss. In June 2015, the FDA issued a Safety Alert stating that there was no evidence for treatment associated vision loss following a review. In keeping with FDA recommendations, study participants undergo full ophthalmological exams at screening and study exit. For more information please refer to sections 5.3 “Safety evaluations” and 9 “Study procedures and guidelines.”

Potential for Unforeseen Risks:

In addition to these risks there may be other risks associated with ezogabine, which are currently unknown as the study drug has never been used on a sample of anhedonic subjects with mood and anxiety disorders. Data from our pilot study show that ezogabine was well tolerated, no subjects discontinued the treatment protocol, no SAEs and no unexpected AEs occurred.

Potential for Harms Unrelated to Study Drug:

The following additional sources of potential discomfort or harm could also occur:

- **Psychological Screening:** Subjects that meet exclusion criteria (e.g. positive pregnancy test) may become distressed when informed. All information will be shared in a private office with the door closed and a trained study team member will be available to offer information, support, and referral for any services indicated.
- **Medical Screening:** Participants may experience minor discomfort or pain when a needle is used to draw blood. Bruising, infection, and dizziness are also common side effects. Risks of venipuncture are minimized by having experienced nursing personnel who will perform the procedure. Infection is avoided by adequate cleansing of the skin prior to intravascular line insertion.

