8 STUDY TREATMENTS

8.1 Method of Assigning Subjects to Treatment Groups

Central randomization will be implemented in this study by the coordinating site. Forty-eight eligible patients will be randomly assigned to ezogabine (900 mg/day; n=24) or placebo treatment (n=24) groups in a 1:1 ratio using a computer-generated randomization scheme developed by the coordinating site. The randomization will be balanced by using randomly permuted blocks. The interactive web response system (IWRS) will assign a unique treatment code, which will dictate the treatment assignment and matching study drug kit for the subject.

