8.4.1 Dosage/Dosage Regimen

Titration Period. Study drug titration will follow the guidelines contained within the FDA package insert and will not exceed the maximum approved dose for partial-onset seizures (1,200 mg daily). For this study, a daily dose of 900 mg has been selected, along with placebo.

For the ezogabine arm, participants start at 100 mg 3 times daily (300 mg per day) and increase at weekly intervals by 150 mg (50 mg 3 times per day) up to a stable dosage of 900 mg daily. A 150 mg increase each week is the maximum increase recommended by the FDA. Those assigned to receive placebo will receive capsules containing an inactive compound at a frequency comparable to those in active treatment (i.e., 1 capsule, 3 times per day). Dose titration will be conducted based on subject tolerability.

Subjects who are unable to tolerate a protocol-specified dose increase will be retained in the study at the highest tolerated dose for that subject through to the Primary Outcome Visit (V5), before beginning to taper off of the medication. In the event that a subject experiences a potential dose-dependent adverse medication effect in the opinion of the investigator, the subject will be maintained at the subject's highest previously tolerated dose. One dose reduction for the purpose of resolving suspected medication-related adverse effects will be allowed per subject. Subjects who continue to experience tolerability issues despite the dose reduction will initiate the taper phase and will be exited early from the study protocol. The taper schedule will follow procedures reported in section 10.5 "Taper Period" and section 10.6 "Study Exit Visit" (Visit 6) and early withdrawal". All available data for each subject will be included in the statistical analyses, including from subjects who discontinue early for any reason. Study subjects who discontinue early for any reason, however, will not be replaced. During the trial, the following dosages of ezogabine will be used: 50 mg, 200 mg and 300 mg. To assure the blindness of the trial, the research pharmacist at each site will encapsulate every pill so that all study pills regardless of dosage will look identical.

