Clinical Global Impression - Improvement (CGI-I): this is a widely administered clinician rated global measure of the degree of improvement from the initial assessment in subject overall illness severity. Subjects are rated on a 1-7 scale where 1 corresponds to “Very Much Improved”, 2 is “Much Improved”, the anchor for 3 is “Minimally Improved”, the anchor for 4 is “No Change”, 5 is “Minimally Worse”, 6 is “Much Worse”, and 7 is “Very Much Worse”. It will be administered at all subject visits. During the course of the trial subjects for whom the CGI-I is greater than 5 will be removed from the study and appropriate care given, for safety purposes.

Columbia-Suicide Severity Rating Scale (C-SSRS): The Columbia-Suicide Severity Rating Scale (C-SSRS) (Posner et al., 2007) is a comprehensive, semi-structured interview that uniquely measures the full spectrum of suicidality including passive and active suicidal ideation, suicidal intent as well as suicidal behaviors. Subjects will be assessed at every visit with the CSSRS by a qualified rater. Study participants will meet with a study physician at each study visit, which will include a review of the C-SSRS. Any subject with an increase in suicidality and all those subjects found to have a plan or intent will undergo thorough assessment by the study psychiatrist. If, at any point during the clinical trial, a participants will be assessed by the study physician with a suicidal ideation with any intent or plan, as measured by a C-SSRS score of greater than 3 during the past week and with either a GCI-S score ≥ 6 (indicating extreme illness severity) or a CGI-I score ≥ 6 (indicating an extreme worseness of the symptoms), the site PI, or his designee, will conduct a safety review to determine the appropriate course of action including whether acute intervention is needed and whether it is in the best interests of the subject to continue in the study. For more details regarding the safety review procedures, please refer to section 5.3 “Safety evaluation”.

Behavioral assessment

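### The weekly clinician and suicidality check promised during treatment has no scheduled contact behind it when Visit 5 falls more than 10 days after Visit 4

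*Protocol*

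**What the plan says.** Protocol section 5.3 states: "Participants will meet with a study clinician weekly during the treatment period". It adds that suicidal ideation and behaviour are specifically assessed at these meetings. Section 2.1 (Suicidality) describes the monitoring as "clinical assessments at screening and exit visits, and weekly during the treatment period", with the C-SSRS given at each study visit.

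For dosing, section 8.4.1 has participants start at 300 mg daily and "increase at weekly intervals by 150 mg (50 mg 3 times per day) up to a stable dosage of 900 mg daily". Section 10.3 confirms that participants have had a week at 750 mg when they reach V4 and go up to 900 mg from there. The QT paragraph of section 2.1 says that "participants will be at the highest dose of 900 mg per day, respectively, for one week".

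For timing, section 10 gives visits a window of 3 days either side but excepts V5. V5 may take place once the participant has spent 7 to 14 days on the highest tolerated dose. Section 10.4 repeats this and does not let the taper start before V5 is complete. The Table 2 footnote counts the same one to two weeks from V4. Section 10 and Table 2 show no visit or call between V4 and V5. The phone calls in section 10.5 begin only after V5.

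**The concern.** A site can follow the visit schedule exactly and still not deliver the weekly check that sections 2.1 and 5.3 promise. The gap comes at a sensitive time. For anyone who starts 900 mg at V4, it follows the last dose increase directly. Participants are depressed, and section 2.1 itself cites a suicidality signal for antiepileptic drugs as a class (adjusted relative risk 1.8, 95% CI 1.2 to 2.7). At stake is how soon worsening or new ideation is noticed. The trial's endpoints are not involved.

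**Working it through.** **Inputs.** Start 300 mg daily, weekly step 150 mg, target 900 mg (section 8.4.1). V1 to V4 at weeks 1 to 4, each within 3 days (section 10.3). V5 after 7 to 14 days on the highest tolerated dose (sections 10 and 10.4), or one to two weeks from V4 (Table 2 footnote). Scheduled contacts between V4 and V5: none.

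**1. When 900 mg starts.** Steps needed = (900 − 300) / 150 = 4, so 900 mg starts at V4, nominal day 4 × 7 = 28.

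**2. The plan's own figure.** With V5 at week 5 (day 35), time at 900 mg = 35 − 28 = 7 days. This reproduces the one week in section 2.1.

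**3. The permitted range.** V5 = V4 + 7 to V4 + 14.
- V4 on day 28: V5 on days 35 to 42.
- V4 on day 25 (3 days early): V5 on days 32 to 39.
- V4 on day 31 (3 days late): V5 on days 38 to 45.

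Time at 900 mg before V5 is 7 to 14 days in each case, so one week is the minimum and the maximum is twice that.

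**4. Whether a check is missed.** Let d be the days from V4 to V5. A weekly check is due at V4 + 7. With the 3-day tolerance that the protocol gives its other visits, it may fall from day 4 to day 10 after V4.
- d = 7: on time.
- d = 8 to 10: late, but within tolerance; V5 itself serves as the check.
- d = 11 to 14: nothing falls in the window, so that week's check does not take place.

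At d = 14 the gap is 14 − 7 = 7 days beyond weekly, and 14 − 10 = 4 days beyond weekly plus tolerance.

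**5. Comparison with V1 to V4.** Two consecutive visits can be 7 + 3 + 3 = 13 days apart, but each week still has its own scheduled visit. Between V4 and a late V5 it does not.

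**6. Who is affected.**
- Participants who start 900 mg at V4: both counting rules give d = 7 to 14.
- Participants held at 750 mg since V3 (nominal day 21): counted from the dose, V5 falls on days 28 to 35, so nominally d = 0 to 7 and no check is missed. Counted from V4, d = 7 to 14 and one can be missed. For them the gap does not directly follow a dose increase, because V4 with its C-SSRS comes in between.
- Participants with a QT finding at V4: section 10.3 has them taper and return after one week, so the gap does not arise.

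**The case against.** The strongest reply is that the treatment period means the five planned weeks. The synopsis gives five weeks for titration and treatment, section 4.1 describes weekly assessments over five weeks, and V1 to V5 supply five checks. The extra days before V5 are then a scheduling allowance for the scan. That is a fair reading of the calendar, but the participant is still taking the highest tolerated dose until V5, so the reason for a weekly check has not ended.

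A second reply is that gaps of 13 days are already possible between V1 and V4, so 14 days is only one day worse. That is true of the length. The difference is that no visit at all is assigned to the second week after V4 begins to run over.

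Several stronger readings are tempting, and the documents do not support them:
- **Any V5 later than day 7 omits a check.** The 3-day tolerance makes days 8 to 10 a late check.
- **Section 2.1's weekly physician evaluation is a further broken promise.** The statement "subjects will be evaluated on a weekly basis by a study physician" concerns dizziness and somnolence during titration and adds little here.
- **Participants are held on drug without a way out.** Section 8.4.1 allows a dose reduction and early taper, and section 12.1 allows discontinuation at any time.
- **Ideation early in the gap would be lost at V5.** One limb of the safety-review trigger is indeed worded "as measured by a C-SSRS score of greater than 3 during the past week". But section 9.1.6 separately says "Any subject with an increase in suicidality and all those subjects found to have a plan or intent will undergo thorough assessment", with no such time limit. A change to the look-back at V5 alone would also leave V1 to V4 on a different rule.
- **The QT argument fails.** One week is the nominal duration, and the dose stays at 900 mg, below the 1,200 mg at which the cited QT effect was seen.

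**Conclusion.** The inconsistency is real and minor. When V5 is more than 10 days after V4, one promised weekly clinician and suicidality check is not scheduled. The longest permitted interval without a check is 14 days. For participants who start 900 mg at V4, that interval directly follows the last increase.

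The consequence is later detection. At V5 the C-SSRS, the CGI scales, the interval history and the diary review still apply, as does the psychiatrist's assessment. Endpoints and analysis are unaffected.

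The conclusion rests on two assumptions: that weekly monitoring is meant to continue while the participant is on study drug, and that the 3-day tolerance for other visits is a fair allowance for this check. The documents give no distribution of V5 dates, so neither the number of participants affected nor a number of late-detected events can be stated.

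**What to change.** Add a footnote to Table 2: if V5 is or will be more than 10 days after V4, one clinician contact takes place about 7 days after V4 (within 3 days), by phone or in person, with adverse-event review and a C-SSRS by a qualified rater. State in section 5.3 that a phone contact satisfies that week's meeting. The research coordinator's taper calls in section 10.5 are not a model for this contact, since it needs a clinician and a qualified C-SSRS rater.

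In section 2.1, change the stated time at 900 mg from one week to 7 to 14 days. This is a wording correction only.

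The cost is one footnote, one sentence and one wording edit, plus at most one short contact by existing staff for each affected participant. The V5 scan window keeps its flexibility, and the rule is the same in both arms, so the blind is not affected.
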